**16.33 Correlative Analysis**

16.331 BTK signaling proteins (western blot and densitometric quantification) and gene expression (quantitative real-time PCR) will be examined in CD19/CD138+ WM cells collected from patients on the study. 15 protein/genes associated with BTK-signaling will be assessed and their levels from baseline samples will be compared with levels from samples during treatment. Changes over time will be evaluated using paired

sample approaches (Wilcoxon signed rank test). Baseline levels will be correlated with response (responder vs. non-responder) using Wilcoxon rank sum tests.

16.332 Exploration of the biologic effects of ibrutinib and ixazomib on microenvironment in WM will include 3 types of data:

- Immunophenotyping of tumor infiltrating lymphocytes (TILs) using the Multi-Omyx TILs platform. This will identify 17 different types of TILs from BM samples collected at baseline and then after one cycle of treatment. This data is represented as % and actual cell counts.
- Identification of 4 types of T-cells from the blood. This will be done from peripheral blood samples collected at Baseline and then after one cycle of treatment with Ixa+Ibr.
- BTK receptor occupancy: This is a competitive-binding assay essentially and will be performed in CD19+/CD138+ WM cells collected at baseline and then after one cycle of treatment with Ixa+Ibr. Readout is % occupancy

Values will be correlated with response (responder vs. non-responder) using Wilcoxon rank sum tests.

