#### 1.5 Correlative Research

1.51 *To determine the role of members of the BTK signalosome in achievement or lack thereof of response to Ibrutinib and Ixazomib:* The variability in extent of response to a therapeutic agent may suggest underlying adaptability of the WM clone through components of the BTK signalosome. Patients with B-cell malignancies treated with ibrutinib demonstrate upregulation of p-Akt and p-Erk (downstream mediators of BTK) in some (but not all) cases, suggesting that these pathways may contribute to survival of the malignant clone. It was also concluded in this work that these cells might not be dependent upon the proximal BTK pathways mediated apoptosis and thus, resistant to killing by Ibrutinib. To address this question we will establish the profile of BTK signalosome for each patient through determination of the mRNA (RT-PCR/nanostring assay; whole exome sequencing (WES), transcriptome analysis) and protein expression (western blot analysis) of members of the BTK signaling pathway and look for associations between this and eventual response (or lack thereof) to the treatment. The said tests will be done analyzing the lymphoplasmacytic cells enriched from the bone marrow samples collected at baseline, and then at the time of disease progression. This will help explore mechanisms of acquired resistance to ibrutinib when used with ixazomib. We will also look for pAkt, pS6 and pERK as indirect pharmacodynamic biomarkers analyzed in patient's PBMC collected as a peripheral blood sample.

1.52 *To explore biologic effects of ibrutinib and ixazomib on microenvironment in WM and correlate with response to treatment:* In cancer redirection of host immunity from a predominant Th2 to Th1 response can deliver antitumor response. Ibrutinib can

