bind to ITK, a member of the TEC-kinase family, which mediates TCR signaling through PLC $\gamma$ , NFAT, NF- $\kappa$ B and MAPK. This results in activation and proliferation of CD8 $+$  cells. Our hypothesis is that ibrutinib with ixazomib alters the Th2:Th1 balance in the blood and bone marrow microenvironment, skewing towards a more Th1 profile and this may translate into clinical efficacy. We further hypothesize that the robustness of the Th1 response will direct this combination's depth of response. We will assess this in bone marrow samples comparing the baseline sample to one collected after 1 cycle of treatment with ibrutinib and ixazomib using the MultiOmyx Tumor Infiltrating Lymphocytes panel for T helper (CD4 $+$ ), Treg (FOXP3 $+$ ), T cytotoxic (CD8 $+$ ), B cells (CD20 $+$ ), macrophage (CD68 $+$ ), NK cells (CD56 $+$ ), immunosuppression (PD-L1), CD138 $+$ , CD38 $+$ , ITK and BTK. Furthermore, BTK/ITK occupancy by Ibrutinib has been associated with response rates in other B-cell malignancies where this is an effective agent (CLL) but this has never been tested in WM. This assay will be performed to assess target coverage in bone marrow samples obtained from patients at the end of 1 cycle of treatment with ibrutinib and ixazomib. In addition, PBMC samples (2 ml of whole blood with heparin) from baseline and after 1 cycle of treatment will be assessed for:

Th1 cells (live $+$ , CD19 $-$ , CD3 $+$ , CD4 $+$ , CD8 $-$ , IFNg $+$ )

Th2 cells (live $+$ , CD19 $-$ , CD3 $+$ , CD4 $+$ , CD8 $-$ , IL4 $+$ )

Th17 cells (live $+$ , CD19 $-$ , CD3 $+$ , CD4 $+$ , CD8 $-$ , IL17 $+$ )

Treg cells (live $+$ , CD19 $-$ , CD14 $-$ , CD3 $+$ , CD4 $+$ , CD25 $+$ , CD127 $-$ , FOXP3, CCR4 $+$ )

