### **2.3 Correlative Research**

- 2.31 To determine the role of members of the BTK signalosome in achievement or lack thereof of response to ibrutinib and ixazomib.
- 2.32 To explore biologic effects of ibrutinib and ixazomib on microenvironment in WM and correlate with response to treatment.

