## 11.0 Treatment Evaluation/Measurement of Effect

### 11.1 Terms and definitions

- **M-protein:** synonyms include M-spike, monoclonal protein and myeloma protein, paraprotein, M-component.

Serum M-protein level is quantitated using densitometry on SPEP except in cases where the SPEP is felt to be unreliable.

- M-proteins migrating in the  $\beta$ -region (usually IgA M-proteins)
- Cases in which the M-protein is so large and narrow on agarose (some specimens  $>4$  g/dL) that they underestimate the actual immunoglobulin level (by greater than 1500 mg/dL) due to technical staining properties of the agarose gel.
- Cases in which there are multiple peaks of same M-protein (aggregates or dimers).

If SPEP is not available or felt to be unreliable (above examples) for routine M-protein quantitation, then quantitative immunoglobulin levels derived from nephelometry or turbidometry can be accepted, with the exception that quantitative IgG may not be used. However, this must be explicitly reported at baseline, and only nephelometry can be used for that patient to assess response. SPEP derived M-protein values and quantitative nephelometric immunoglobulin values cannot be used interchangeably.

Urine M-protein measurement is estimated using 24-h UPEP only. Random or 24 h urine tests measuring kappa and lambda light chain levels are not reliable and are not recommended.

- **FLC estimation** is currently carried out using the serum FLC assay (Freelite, The Binding Site Limited, UK). Patients with kappa/lambda FLC ratio  $<0.26$  are defined as having monoclonal lambda FLC and those with ratios  $>1.65$  as having a monoclonal kappa FLC. The monoclonal light chain isotype is considered the involved FLC isotype, and the opposite light chain type as the uninvolved FLC type.

**Response terms:** The following response terms will be used: complete response (CR), Very Good Partial Response (VGPR), Partial Response (PR), Minor Response (MR), Stable Disease (SD), and Progressive Disease (PD). (APPENDIX III)

An objective status of CR is defined as (See Appendix III):

- Absence of serum monoclonal IgM protein by immunofixation
- Normal serum IgM level
- Complete resolution of extramedullary disease, i.e. lymphadenopathy and splenomegaly if present at baseline
- Morphologically normal bone marrow aspirate and trephine biopsy (*ref: Owen 2013*)
- No signs or symptoms attributable to WM

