### Appendix III Response Assessment Criteria

Response	Criteria
Complete response	
 
• Absence of serum monoclonal IgM protein by immunofixation
 
• Normal serum IgM level
 
• Complete resolution of extramedullary disease, i.e., lymphadenopathy (resolution to <math>\leq 1.5</math> cm in longest diameter of all nodes) and splenomegaly/hepatomegaly if present at baseline
 
• Morphologically normal bone marrow aspirate and trephine biopsy
 
• No signs or symptoms attributable to WM
 
 
Confirmation of the complete response status is required on two consecutive evaluations with a second immunofixation before reporting an objective status of CR

Very good partial response	
 
• Monoclonal IgM protein is detectable
 
• <math>\geq 90\%</math> reduction in serum IgM level from baseline
 
• Complete resolution of extramedullary disease, i.e., lymphadenopathy (resolution to <math>\leq 1.5</math> cm in longest diameter of all nodes) and splenomegaly/hepatomegaly if present at baseline
 
• No new signs or symptoms of active disease
 

Partial response	
 
• Monoclonal IgM protein is detectable
 
• <math>\geq 50\%</math> but <math>< 90\%</math> reduction in serum IgM level from baseline
 
• <math>\geq 50\%</math> reduction in extramedullary disease, i.e., <math>\geq 50\%</math> reduction in SPD from baseline for lymphadenopathy and <math>\geq 50\%</math> reduction from baseline in splenomegaly/hepatomegaly if present at baseline
 
• No new signs or symptoms of active disease
 

Minor response	
 
• Monoclonal IgM protein is detectable
 
• <math>\geq 25\%</math> but <math>< 50\%</math> reduction in serum IgM level from baseline
 
• No new signs or symptoms of active disease
 

Stable disease	
 
• Monoclonal IgM protein is detectable
 
• <math>< 25\%</math> reduction and <math>< 25\%</math> increase in serum IgM level from baseline
 
• No progression in extramedullary disease, i.e., lymphadenopathy/splenomegaly/hepatomegaly
 
• No new signs or symptoms of active disease
 

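### Section 16.332 tests the microenvironment markers only by responder against non-responder, although the stated Th1 hypothesis concerns depth of response

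*Combined protocol and SAP*

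**What the plan says.** Section 1.52, repeated in 14.23, sets out the microenvironment work and states: "We further hypothesize that the robustness of the Th1 response will direct this combination's depth of response". The formal goal in 2.32 is more general: "To explore biologic effects of ibrutinib and ixazomib on microenvironment in WM and correlate with response to treatment".

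Section 16.332 lists three data types: tumor-infiltrating lymphocytes in marrow, four T-cell types in blood, and BTK occupancy. One sentence then covers how all three relate to outcome: "Values will be correlated with response (responder vs. non-responder) using Wilcoxon rank sum tests". Section 16 plans no graded analysis.

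Section 16.33 does not say who counts as a responder. Elsewhere the plan offers two candidates: PR or better (2.21, 16.321) and confirmed CR (16.311).

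Response itself is recorded on a six-level scale from CR to PD (11.1, Appendix III), and the test schedule in 4.1 has immunoglobulins measured at baseline and through treatment.

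The BTK signalosome work is framed differently. Section 1.51 aims to "look for associations between this and eventual response (or lack thereof) to the treatment", and 16.331 plans accordingly: "Baseline levels will be correlated with response (responder vs. non-responder) using Wilcoxon rank sum tests".

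**The concern.** The hypothesis and the test use different outcomes. Depth of response runs from no response through MR, PR and VGPR to CR. A two-group test keeps one cut on that scale and ignores all differences within each side.

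With a cut at PR or better, a patient in PR and a patient in CR count as the same result. Yet Section 1.3 motivates the combination by noting that most ibrutinib responses stop at partial remission. The contrast among PR, VGPR and CR is therefore the one of most interest, and the split does not see it. The comparison also rests on the non-responders, whose number shrinks as the regimen works better.

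At stake is whether the mandatory marrow and blood samples can show the relation proposed in 1.52. A real association of moderate size could be missed although the data to detect it are already collected.

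**Working it through.** **Inputs from the documents.** N = 37 evaluable patients (16.22). Six response levels (11.1, Appendix III), with SD and PD pooled here as the lowest of five ordered groups. Single-agent ibrutinib: VGPR 11.1%, PR 50.8%, no CR, 61.9% in total (1.2). CR rates of 5% and 20% (16.21).

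**Assumptions.** The cut is PR or better. All 37 patients give usable samples. Tests are two-sided at 5%, unadjusted. Marker and latent depth are bivariate normal with correlation 0.4 or 0.5. Category shares beyond those in 1.2 are assumed.

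**Step 1: the plan's own figures.** The plan states no power for any correlative test. The primary-design figures in 16.24 do reproduce. The exact probability of declaring promise at CR 5/10/15/20% is 0.0935/0.4468/0.7512/0.9024, against the stated 0.09/0.45/0.75/0.90. Early stopping, (1−p)^12, gives 0.5404/0.2824/0.1422/0.0687, against 0.54/0.28/0.14/0.07. The primary design is not in question.

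**Step 2: information kept by the cut.** With a share q of non-responders, the local efficiency of a split relative to a fully observed continuous depth is φ(z_q)² / [q(1−q)].

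- Response rate 61.9%, q = 0.381: 0.381² / (0.381 × 0.619) = 0.1452 / 0.2358 = 0.616. (Here φ(z_q) also happens to be 0.381.)
- Response rate 80%, q = 0.20: 0.280² / 0.16 = 0.49.
- Response rate 90%, q = 0.10: 0.1755² / 0.09 = 0.342.

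For ordered categories with shares p_k and mid-ranks m_k, let E_k = φ(lower cut) − φ(upper cut). The efficiency is (Σ m_k E_k)² / Σ p_k (m_k − ½)². For the single-agent mix this is 0.2432² / 0.0711 = 0.831. The split relative to the ordered test is then:

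- 62% response rate: 0.616/0.831 = 0.74; 0.69 to 0.71 when the mix includes CRs.
- 80%: 0.49/0.88 = 0.56.
- 90%: 0.342/0.851 = 0.40 and 0.342/0.770 = 0.44.

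**Step 3: power at N = 37.** Simulation with 4,000 runs per cell: exact Wilcoxon rank sum on the split against Spearman on the five ordered groups. Entries are percentages; loss is ordered minus split, in points.

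| SD-PD / MR / PR / VGPR / CR | PR or better | Corr. 0.4: split, ordered, loss | Corr. 0.5: split, ordered, loss |
|---|---|---|---|
| 20 / 18.1 / 50.8 / 11.1 / 0 | 62 | 46, 59, 13 | 67, 81, 14 |
| 20 / 18.1 / 45.9 / 11 / 5 | 62 | 46, 61, 15 | 67, 82, 15 |
| 20 / 18 / 27 / 15 / 20 | 62 | 45, 61, 16 | 67, 83, 16 |
| 10 / 10 / 40 / 20 / 20 | 80 | 38, 62, 24 | 56, 83, 27 |
| 5 / 5 / 45 / 25 / 20 | 90 | 26, 62, 36 | 37, 81, 44 |
| 5 / 5 / 65 / 20 / 5 | 90 | 25, 53, 28 | 36, 77, 41 |

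With no association the split rejects in 4% to 5% of runs and the ordered test in 5%, so the gain does not come from an inflated error rate.

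A second set of mixes, with response rates of 62%, 75% and 85%, was simulated repeatedly. It gave 29% to 48% (split) against 59% to 64% (ordered) at correlation 0.4, and 47% to 67% against 80% to 85% at 0.5.

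**Step 4: if responder means CR.** Power of the split is 36% to 37% (correlation 0.4) and 55% (0.5) at a CR rate of 20%. At a CR rate of 5% it is 13% to 15% and 20% to 21%, and about 15% of trials would have no CR to compare (0.95^37 = 0.150). With the single-agent mix, which has no CRs, the test cannot be computed.

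**The case against.** The best defence is that the split matches the goals as written. Goal 2.32 speaks only of correlating with response, and a monotone relation with depth would also separate responders from non-responders. The planned test therefore answers a coarser form of the same question. That stands. It does not answer the explicit depth hypothesis in 1.52 and 14.23, which no other analysis addresses.

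A reader might extend the criticism to 16.331. The documents do not support that. Goal 2.31 and Sections 1.51 and 14.22 ask about response or its absence, which a binary test fits. The background there mentions variable extent of response, so an ordered test is a reasonable option but not a correction.

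A reader might also infer that the split has far less power in general. That depends on the scenario. With the only response distribution in the documents, about 14 of 37 patients (37 × 0.381) are non-responders and the loss is moderate. At correlation 0.3 the ordered test is weak too: 34% to 38%, against 15% to 28% for the split at PR or better.

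Finally, a reader might infer that the many markers require formal multiplicity control. Section 16.332 describes itself as exploration, and no decision rule uses its results. Adjustment would also cost power. With a single true marker at correlation 0.4, a Benjamini-Hochberg adjustment takes the ordered test from 59–61% to roughly 38–40% in a family of 4 and 21–23% in a family of 17. That is a trade-off for the sponsor, not part of this point.

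**Conclusion.** The point holds for 16.332. The only planned outcome analysis of the microenvironment markers is a two-group test, while the stated Th1 hypothesis is about depth of response. On a PR-or-better cut, the differences among PR, VGPR and CR are ignored.

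The ordered test had more power in every mix tried. At correlations of 0.4 to 0.5 and response rates of 62% to 85%, the range is about 30% to 67% for the split and 59% to 85% for the ordered test. The gap is 13 to 16 points at a response rate of 62%, 24 to 27 at 80% and 28 to 44 at 90%.

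These sizes rest on the assumed cut, a latent-normal monotone association, the assumed correlations and response mixes, 37 usable samples and unadjusted tests. The mismatch itself rests on none of them. It would be too strong to say that the correlative goals cannot be met: neither 2.31 nor 2.32 mentions depth. The work is exploratory, and the primary CR decision is unaffected.

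**What to change.** In 16.332:

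- Make the main analysis of the Th1 and other microenvironment markers a trend test against ordered best response (SD/PD < MR < PR < VGPR < CR), using Spearman correlation or Jonckheere-Terpstra.
- Add correlation with maximum percent IgM reduction as support.
- Keep the two-group rank-sum test as descriptive, and state whether a responder means PR or better or confirmed CR.
- While the sentence is open, it would help to say whether the baseline value, the value after cycle 1 or the change is tested; the text does not say.

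Section 16.331 can keep its binary test, with the same definition of responder. An ordered test there is optional.

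The cost is SAP wording and one changed exploratory analysis. Response category and IgM are already collected, so no sample, visit or patient is added.

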#### **16.4 Early Safety Analysis**

7.1 An early safety analysis will be performed after the first 6 evaluable patients have been accrued to the study and observed for one cycle. Accrual will be temporarily halted while these patients are evaluated. If 2 or more of the first 6 patients experience a significant toxicity as defined below, then the dose of ixazomib may be de-escalated (as per Table b). In this case, another safety analysis will be conducted on the first 6 evaluable patients treated at the reduced dose level.

Toxicity will be measured per NCI-CTCAE version 4. Significant toxicity is defined as an adverse event occurring during the first cycle of treatment that is possibly, probably, or definitely related to study treatment and that meets one of the following:

- Grade 3 diarrhea, nausea, and fatigue lasting > 3 days despite optimal supportive medications
- Any other  $\geq$  Grade 3 non-hematological toxicity with the exceptions of electrolyte abnormalities that are reversible and asymptomatic.
- Febrile neutropenia
- Grade 3 thrombocytopenia with clinically significant bleeding
- Any  $\geq$ Grade 4 neutrophil count decreased or platelet count decreased that persists >7 days

#### **16.5 Data & Safety Monitoring**

16.51 The principal investigator(s) and the study statistician will review the study at least twice a year to identify accrual, AE, and any endpoint problems that might be developing. The Mayo Clinic Cancer Center (MCCC) Data Safety Monitoring Board (DSMB) is responsible for reviewing accrual and safety data for this trial at least twice a year, based on reports provided by the MCCC Statistical Office.

#### **16.52 Adverse Event Stopping Rules**

The stopping rules specified below are based on the knowledge available at study development. We note that the AE Stopping Rule may be adjusted in the event of

either (1) the study re-opening to accrual or (2) at any time during the conduct of the trial and in consideration of newly acquired information regarding the AE profile of the treatment(s) under investigation. The study team may choose to suspend accrual because of unexpected AE profiles that have not crossed the specified rule below.

Accrual will be temporarily suspended to this study if at any time we observe events considered at least possibly related to study treatment (i.e. an AE with attribute specified as “possible,” “probable,” or “definite”) that satisfy one of the following:

- if 4 or more patients in the first 12 treated patients experience a grade 4 or higher non-hematologic AE at least possibly related to treatment.
- if after the first 12 patients have been treated, 30% of all patients experience a grade 4 or higher non-hematologic AE at least possibly related to treatment.

We note that we will review grade 4 and 5 AEs deemed “unrelated” or “unlikely to be related”, to verify their attribution and to monitor the emergence of a previously unrecognized treatment-related AE.

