#### 10.32 EXPECTED Serious Adverse Events: Protocol Specific Exceptions to Expedited Reporting

For this protocol only, the following Adverse Events/Grades are expected to occur within this population and do not require Expedited Reporting. These events must still be reported via Routine Reporting (see Section 10.6).\*

\*Report any clinically important increase in the rate of a serious suspected adverse reaction (at your study site) over that which is listed in the protocol or investigator brochure as an expedited event.

\*Report an expected event that is greater in severity or specificity than expected as an expedited event.

\*Specific protocol exceptions to expedited reporting should be reported expeditiously by investigators **ONLY** if they exceed the expected grade of the event.

System Organ Class (SOC)	Adverse event/ Symptoms	CTCAE Grade at which the event will not be reported in an expedited manner 
Blood and lymphatic system disorders	Anemia	≤Grade 4
Gastrointestinal	Vomiting	≤Grade 3
	Nausea	≤Grade 3
	Diarrhea	≤Grade 3
General disorders and administrations site conditions	Fatigue	≤Grade 3
Investigations	Lymphocyte count decreased	≤Grade 4
	Neutrophil count decreased	≤Grade 4
	Platelet count decreased	≤Grade 4
	White blood cell count decreased	≤Grade 4

 These exceptions only apply if the adverse event does not result in hospitalization. If the adverse event results in hospitalization, then the standard expedited adverse events reporting requirements must be followed.

The following hospitalizations are not considered to be SAEs because there is no “adverse event” (*i.e.*, there is no untoward medical occurrence) associated with the hospitalization:

- Hospitalizations for respite care
- Planned hospitalizations required by the protocol
- Hospitalization planned before informed consent (where the condition requiring the hospitalization has not changed post study drug administration)
- Hospitalization for elective procedures unrelated to the current disease and/or treatment on this trial
- Hospitalization for administration of study drug or insertion of access for administration of study drug
- Hospitalization for routine maintenance of a device (*e.g.*, battery replacement) that was in place before study entry
- Hospitalization, or other serious outcomes for signs and symptoms of progression of the cancer.

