#### 15.17 Known Potential Adverse Events

See the current version of the Investigator's Brochure for more complete information including potential risks, as well as recommendations for clinical monitoring and medical management of toxicity. There are no human data available for potential effect of ixazomib on pregnancy or development of the embryo or fetus; however, embryo-fetal studies in animals have demonstrated that ixazomib has the potential to cause lethality.

**Very common ( $\geq 10\%$ ):** peripheral edema, skin rash, constipation, diarrhea, nausea, vomiting, neutropenia, thrombocytopenia, peripheral neuropathy, peripheral sensory neuropathy, back pain, eye disease, upper respiratory tract infection.

**Common ( $\geq 1\%$  to  $< 10\%$ ):** Herpes zoster, hepatic insufficiency, blurred vision, conjunctivitis, xerophthalmia, pneumonia ,

**Uncommon ( $< 1\%$ ) or case reports:** cholestatic hepatitis, hepatocellular hepatitis, hepatotoxicity, liver steatosis, peripheral motor neuropathy, reversible posterior leukoencephalopathy syndrome, Stevens-Johnson syndrome, Sweet's syndrome, thrombotic thrombocytopenic purpura, transverse myelitis, tumor lysis syndrome, thrombotic microangiopathy

**Herpes zoster** – antiviral prophylaxis should be considered in patients being treated with Ixazomib to decrease the risk of herpes zoster reactivation.

**Overdose** – There is no known specific antidote for ixazomib overdose. Symptoms of overdose are generally consistent with the known risks of ixazomib and reports have been associated with serious adverse events such as nausea, aspiration pneumonia, multiple organ failure, and death. In the event of an overdose in blinded studies, study medication assignment should be unblinded immediately. The clinician should consider admitting the patient to the hospital for IV hydration, monitoring for adverse drug reactions, monitoring of vital signs, and appropriate supportive care. Gastric lavage may be considered, but it should be kept in mind that ixazomib absorption is rapid. Ixazomib is not readily dialyzable.

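### The accrual-suspension rule in Section 16.52 has no exception for grade 5, so a treatment-related death coded to a hematologic term would not count toward either limit

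*Combined protocol and SAP*

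**What the plan says.** Section 16.52 opens its rule with "Accrual will be temporarily suspended to this study if at any time we observe events considered at least possibly related to study treatment" and gives two limbs. The first applies "if 4 or more patients in the first 12 treated patients experience a grade 4 or higher non-hematologic AE". The second applies once 12 patients have been treated, when "30% of all patients experience a grade 4 or higher non-hematologic AE at least possibly related to treatment". Neither limb treats grade 5 separately, and the section contains no hematologic trigger. The same section leaves room for judgement: "The study team may choose to suspend accrual because of unexpected AE profiles that have not crossed the specified rule below". It also has grade 4 and 5 events judged unrelated or unlikely reviewed, to verify attribution and "to monitor the emergence of a previously unrecognized treatment-related AE".

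Section 16.4 sets a different rule for cycle 1 of the first 6 evaluable patients, repeated in 6 patients if the ixazomib dose is reduced. Its trigger is 2 or more patients with significant toxicity. Its list has one item for other non-hematological toxicity of grade 3 or higher and a separate item, "Febrile neutropenia". It also counts defined severe cytopenias.

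Section 15.17 lists "thrombotic thrombocytopenic purpura, transverse myelitis, tumor lysis syndrome, thrombotic microangiopathy" among the uncommon ixazomib risks, and Section 15.209b names TTP among rare life-threatening conditions. Neither says whether TTP is hematologic. Section 16.214 gives the existence of an AE stopping rule as one reason for not pausing accrual at the interim analysis.

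**The concern.** A rule that leaves out hematologic events usually does so to avoid halting a trial for laboratory cytopenias that are expected and manageable. That reason does not extend to a death. As written, the exclusion rests on a class label alone, so two related deaths can be treated differently according to the term each is coded to.

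This matters here for two reasons. First, Section 15 lists neutropenia and reduced platelets for both drugs, treatment runs up to 24 cycles, and Section 16.4 covers only cycle 1 of 6 patients at a dose level. After that, Section 16.52 is the only safety rule with a number in it. Second, because Section 16.214 leans on the rule to justify continued accrual, what the rule counts is part of the argument for the design.

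**Working it through.** The documents give no assumed AE rate and no operating characteristics for this rule, so there is no stated figure to reproduce. The check has a textual part and an arithmetical part.

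**1. Which side of the line each event falls on**

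| Event | Evidence in the protocol | Counts in 16.52? |
|---|---|---|
| Isolated count decreases, anemia | Section 10.32 treats them as expected up to grade 4 | No, reasonably |
| Febrile neutropenia, including fatal | Section 16.4 lists it apart from other non-hematological toxicity; Table 8.2 handles it at grade 3 or higher, so the separate item would be redundant if it were non-hematologic | No, on the natural reading |
| TTP | Listed in 15.17 and 15.209b without a class | Undetermined |
| Death attributed to a non-hematologic term | Section 10.52 assigns deaths to a CTCAE term where possible | Yes, if related |

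The organ-class column of Table 8.2 is weaker evidence. It puts febrile neutropenia under blood and lymphatic disorders, but it puts neutrophil and platelet decreases under investigations, so organ class cannot be the dividing line the protocol has in mind.

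**2. A literal count**

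Suppose that among the first 12 treated patients, 3 have related grade 4 non-hematologic AEs and a fourth dies of related febrile neutropenia. The count as written is 3, below 4, and accrual is not suspended. If related grade 5 events of any class counted, it would be 4 and accrual would be suspended.

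**3. Effect on the first limb**

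Inputs: n = 12 and limit 4 (Section 16.52). Assumptions, not in the documents: q is the proportion of patients with a related non-hematologic AE of grade 4 or higher; e is the proportion with an additional hematologic event that would count after the change, independent of the first.

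Formulas: p = 1 − (1 − q)(1 − e), and P(X ≥ 4) = 1 − Σ C(12,k) p^k (1 − p)^(12−k), summed over k = 0 to 3.

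For q = 0.20:

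- e = 0: p = 0.200. P = 1 − (0.0687 + 0.2062 + 0.2835 + 0.2362) = 0.2054.
- e = 0.01: p = 1 − 0.80 × 0.99 = 0.208. P = 1 − (0.0609 + 0.1920 + 0.2773 + 0.2427) = 0.2271.
- e = 0.03: p = 1 − 0.80 × 0.97 = 0.224. P = 1 − (0.0477 + 0.1652 + 0.2622 + 0.2523) = 0.2726.

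The same formulas at other base rates:

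| q | As written (e not counted) | e = 1% counted | e = 3% counted |
|---|---|---|---|
| 5% | 0.0022 | 0.0042 | 0.0112 |
| 10% | 0.0256 | 0.0341 | 0.0555 |
| 15% | 0.0922 | 0.1084 | 0.1447 |
| 20% | 0.2054 | 0.2271 | 0.2726 |

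As written, the probability stays in the second column whatever e is. Higher added rates give larger gaps (at q = 20%, 0.3205 for e = 5% and 0.4452 for e = 10%), but nothing in the documents supports rates that high. The only frequency given for TTP is below 1%, and febrile neutropenia is not named in either drug's toxicity list in Section 15.

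**The case against.** The best defence is that the rule does not work alone. Section 16.4 counts febrile neutropenia and certain cytopenias. Section 10.52 requires deaths within 30 days of the last dose, and later related deaths, to be reported within 24 hours. The DSMB reviews safety at least twice a year. Sections 16.214 and 16.22 make continued accrual conditional on the absence of undue toxicity, with no hematologic exclusion, and Section 16.25 brings AEs into any decision to terminate. Section 16.52 itself can be adjusted at any time in the light of new AE information. All of this stands, and it makes it unlikely that a related hematologic death would go unnoticed. But of these only Section 16.4 has a numerical trigger, and it covers cycle 1 of 6 patients at a dose level. The discretionary clause speaks of unexpected profiles, which fits poorly with neutropenic complications of drugs already listed as causing neutropenia.

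A second objection is that counting grade 5 events changes little. With the limits kept, three related hematologic deaths among the first 12 patients and nothing else would still not reach 4. That is true. The change makes the count consistent; it does not create a death rule.

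A reader might infer more than the documents support: that febrile neutropenia and TTP are never counted in any safety rule, or that Section 16.52 departs from an intended count. The first fails because Section 16.4 counts febrile neutropenia and because TTP is unclassified. The second fails because no intended count is stated; excluding hematologic events is a design choice, reasonable for expected cytopenias.

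**Conclusion.** The gap is real but narrow. On its wording, Section 16.52 gives no weight to a treatment-related death coded to a hematologic term, and it leaves events such as TTP to an undefined classification. This conclusion rests on the text and needs no assumed rate, except that placing febrile neutropenia on the hematologic side is inferred from how Section 16.4 sets out its list.

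The size does depend on assumptions. With independent events and a 20% base rate, the chance of reaching 4 of 12 is about 21% as written, against 23% with a 1% added rate and 27% with 3%. At base rates of 5% or 10%, a 1% added rate moves it by less than one percentage point. The plan should be amended because the change is simple and the rule is cited in support of continuing accrual. The gap does not undermine the design.

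**What to change.** In both limbs of Section 16.52, count any grade 5 AE with at least possible attribution to treatment, regardless of organ class. Keep the limits of 4 of 12 and 30%.

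Also define non-hematologic for this rule and reconcile it with Section 16.4, by stating whether febrile neutropenia and other life-threatening hematologic events that are not simple count decreases fall inside it. The list in Section 10.32 should not serve as that definition. It governs expedited reporting, and its exceptions lapse when the event leads to hospitalization, so the same laboratory grade could count or not count depending on admission.

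The cost is one clause and one definition. No new data are needed, because Section 10.62 already collects grade 3 and 4 AEs regardless of attribution and grade 5 AEs. The downside is a slightly higher chance of a temporary accrual pause: roughly 2 percentage points on the first limb at a 20% base rate and 1% added rate, and roughly 7 points at a 3% added rate, both rates being assumed.
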